#### **4.2. Sub-site Enrollment Procedures**

When a potential patient is identified at the sub-site, the Thomas Jefferson University (TJU) Study Site Contact must be contacted within 1 business day via email or phone. Please see the Site Contact List for email and phone number for the TJU Study Site Contact.

1. Notify them of the pending patient registration
2. Email registration documents to TJU Study Site Contact
3. Communicate the desired timeline of the registration.

The sub-site must include the eligibility checklist, signed informed consent, and any applicable documentation supporting eligibility.

Once eligibility has been confirmed locally, TJU will email the Research Coordinator at the sub-site site to confirm patient is eligible and can be enrolled onto the study. The participant will then be assigned a registration number. This number is unique to the participant on this trial and must be used moving forward.

A master study enrollment log will be maintained by the study team at Thomas Jefferson University. The sub-site site will also be asked to maintain an enrollment/screening log on-site, and email this information to the TJU Study Site Contact at least once a month. Patients cannot be registered to this study on the weekends. If a patient is to be registered on a Friday, the sub-site will need to contact the TJU Study Site Contact by Friday at noon at the latest.

If a patient is enrolled at the sub-site without approval from the lead site, TJU will:

- 1) Temporarily suspend the sub-site
- 2) Complete mandatory re-training of staff at the sub-site on the enrollment process. This training will be fully documented.

If enrollment without approval occurs a second time, the sub-site will not be able to continue to participate in this study.

#### **4.3 Strategies for Recruitment and Retention**

Potential subjects with Stage IIB and IIC melanoma will be identified by the examining physician at all sites and referred for evaluation by the principal investigator or one of the co-investigators.

The majority of completed and ongoing melanoma adjuvant clinical trials in the US have involved patients with higher risk stage III disease who are co-managed by medical oncologists, surgical oncologists and dermatology. The enrollment and accrual for these trials were typically driven by medical oncologists with longstanding referral patterns, well-established collaborative groups, and occurred at highly developed Centers of Excellence for melanoma care.

The trial we are proposing is distinct from other adjuvant melanoma trials in that the patients we will enroll are commonly managed primarily by dermatologists and/or surgical oncologists, with less common involvement of medical oncology. Many of these patients never see a medical oncologist unless they develop metastatic disease. Thus, the established mechanisms for the conduct of adjuvant clinical trials in melanoma are not sufficient for this study, and new mechanisms must be put in place to ensure successful accrual. The centers selected for participation in this trial have established melanoma disease management teams that will allow prospective identification of potential candidates by dermatology or surgical oncology, with referral to medical oncology when appropriate. Surgical oncology champions have been identified at each institution to assist with patient recruitment and enrollment.

#### **4.4. Participant Withdrawal**

##### **4.4.1. Reasons for withdrawal**

Participants are free to withdraw from participation in the study at any time upon request.

An investigator may terminate a study participant's participation in the study if:

- Any clinical adverse event (AE), laboratory abnormality, or other medical condition or situation occurs such that continued participation in the study would not be in the best interest of the participant.
- The participant meets an exclusion criterion (either newly developed or not previously recognized) that precludes further study participation.

#### **4.5. Premature Termination or Suspension of Study**

This study may be suspended or prematurely terminated if there is sufficient reasonable cause. Written notification, documenting the reason for study suspension or termination, will be provided by the suspending or terminating party to the investigator, funding agency, the Investigational New Drug (IND) sponsor, and regulatory authorities. If the study is prematurely terminated or suspended, the principal investigator will promptly inform the IRB and will provide the reason(s) for the termination or suspension.

Circumstances that may warrant termination include, but are not limited to:

- Determination of unexpected, significant, or unacceptable risk to participants.
- Insufficient adherence to protocol requirements.
- Data that is not sufficiently complete and/or evaluable.
- Determination of futility.

### **5. STUDY INTERVENTION**

#### **5.1. Study Product**

The study product is nivolumab.

#### **5.2. Study Product Description**

Nivolumab is a highly specific programmed death-1 (PD-1) immune checkpoint inhibitor. The PD-1 receptor is a key regulator of T-cell activity that has been shown to control tumor-specific inhibition of T-cell responses to tumors. Nivolumab is a fully human monoclonal immunoglobulin G4 (IgG4) antibody (HuMAb) that potentiates in vitro T-cell responses through dual ligand blockade of PD-L1 and PD-L2, and does not mediate antibody-dependent cell-mediated cytotoxicity (ADCC). Expression of PD-L1 and PD-L2 by malignant cells or other cells, including immune cells, allows multiple tumor types to evade immune-mediated destruction. Nivolumab restores T-cell activity either by preventing inactivation or by reactivating T cells to mount a direct T-cell immune attack against tumor cells, including an increase in cytotoxic CD8 T cells in the tumor, without any measurable increase in activated circulating T cells peripheral to the tumor.

##### **5.2.1. Acquisition**

Bristol-Myers Squibb (BMS) will provide nivolumab directly to each site.

##### **5.2.2. Formulation, Packaging, and Labeling**

Nivolumab Injection, 100 mg/10 mL (10 mg/mL) is a clear to opalescent, colorless to pale yellow liquid, which may contain light (few) particulates. The drug product is a sterile, non-pyrogenic, single-use, isotonic aqueous solution formulated at 10 mg/mL in sodium citrate, sodium chloride, mannitol, diethylenetriaminepentacetic acid (pentetic acid), and polysorbate 80 (Tween™ 80), pH 6.0 and includes an overfill to account for vial, needle, and syringe holdup. It is supplied in 10-cc Type I flint glass vials, stoppered with butyl rubber stoppers and sealed with aluminum seals. The only difference between the two drug product presentations is the vial fill volume.

### **5.2.3. Product Storage and Stability**

#### Unopened Vial

Vials of nivolumab injection must be stored at 2°C to 8°C (36°F to 46°F) and protected from light and freezing. Do not use nivolumab after the expiry date, which is stated on the carton and on the vial label after EXP. The expiry date refers to the last day of that month.

#### Undiluted Nivolumab Injection and Diluted Nivolumab Injection in the IV Container

The administration of nivolumab infusion must be completed within 24 hours of preparation. If not used immediately, the infusion solution may be stored under refrigeration conditions (2°C to 8°C, 36°F to 46°F) for up to 24 hours, and a maximum of 8 hours of the total 24 hours can be at room temperature (20°C to 25°C, 68°F to 77°F) and room light. The maximum 8 hour period under room temperature and room light conditions includes the product administration period.

### **5.3. Dosage, Preparation, and Administration**

Nivolumab injection is to be administered as an IV infusion through a 0.2-micron to 1.2-micron pore size, low-protein binding (polyethersulfone membrane) in-line filter at the protocol- specified doses and infusion times. It is not to be administered as an IV push or bolus injection. Nivolumab injection can be infused undiluted (10 mg/mL) or diluted with 0.9% Sodium Chloride Injection, USP or 5% Dextrose Injection, USP to protein concentrations as low as 0.35 mg/mL. During drug product preparation and handling, vigorous mixing or shaking is to be avoided. Instructions for dilution and infusion of nivolumab injection may be provided in the clinical protocol, pharmacy binder, pharmacy manual, or pharmacy reference sheet. Care must be taken to assure sterility of the prepared solution as the product does not contain any antimicrobial preservative or bacteriostatic agent. Nivolumab infusions are compatible with polyvinyl chloride (PVC) or polyolefin containers and infusion sets, and glass bottles.

In addition, nivolumab 480 mg administered once every 4 weeks (Q4W) is currently under investigation. The less frequent dosing regimen is designed to afford more convenience to the target patient populations. The nivolumab dose of 480 mg Q4W was selected based on clinical data and modeling and simulation approaches using PPK and exposure-response analyses of data from studies in multiple tumor types (melanoma, NSCLC, and RCC) to provide an approximately equivalent dose of nivolumab 3 mg/kg Q2W. Exposures following nivolumab 480 mg Q4W regimen are predicted to be within the exposure ranges observed at doses up to 10 mg/kg Q2W used in the nivolumab clinical program, and are not considered to put participants at increased risk.

### **5.4. Study Product Accountability**

It is the responsibility of the investigator to ensure that a current record of nivolumab disposition is maintained at each study site where nivolumab is inventoried and disposed. Records or logs must comply with applicable regulations and guidelines, and must include:

1. Amount received and placed in storage area.
2. Amount currently in storage area.
3. Label ID number or batch number and use date or expiry date.
4. Dates and initials of person responsible for each nivolumab inventory entry/movement.
5. Amount dispensed to and returned by each subject, including unique subject identifiers.
6. Amount transferred to another area/site for dispensing or storage.
7. Non-study disposition (e.g., lost, wasted, broken).
8. Amount destroyed at study site.

### **5.5 Dose Modification and Dosing Delays**

Dose modification of nivolumab is not permitted in this study. In some circumstances, it may be

necessary to temporarily interrupt study treatments as a result of AEs that may have an unclear relationship to the study drug.

Treatment must be withheld for drug-related Grade 4 hematologic toxicities, non-hematological toxicity  $\geq$  Grade 3 (including laboratory abnormalities) or selected  $\geq$  grade 2 immune-related toxicities, and severe or life-threatening AEs. Treatment can be held for up to 8 weeks from date of last treatment. If steroids are needed, participant should be treated but if treatment must be withheld for greater than 8 weeks, participant must be permanently discontinued from study treatment.

Table 2 summarizes the dose administration guidance for nivolumab that must be implemented with the indicated related AEs. Additional information related to dose changes for nivolumab for specific AEs can be found subsequently.

Participants may resume treatment with study drug when the drug-related AE(s) resolve to Grade  $\leq 1$  or baseline value, with the following exceptions:

- Participants may resume treatment in the presence of Grade 2 fatigue
- Participants who have not experienced a Grade 3 drug-related skin AE may resume treatment in the presence of Grade 2 skin toxicity
- For participants with Grade 2 AST, ALT and/or Total Bilirubin Abnormalities, dosing may resume when laboratory values return to baseline and management with corticosteroids, if needed, is complete.
- Participants with combined Grade 2 AST/ALT OR total bilirubin values meeting discontinuation parameters must have treatment permanently discontinued.
- Drug-related pulmonary toxicity, diarrhea or colitis must have resolved to baseline before treatment is resumed. Participants with persistent Grade 1 pneumonitis after completion of a steroid taper over at least 1 month may be eligible for retreatment if discussed with and approved by the Lead Study PI.

Participants with drug-related endocrinopathies adequately controlled with only physiologic hormone replacement may resume treatment after consultation with the Lead Study PI. Adrenal insufficiency requires discontinuation regardless of control with hormone replacement.

**Table 2:** Dose Modification Guidelines for Drug-Related Adverse Events

Toxicity	Grade	Hold Treatment (Y/N)	Timing of Treatment Restart	Nivolumab	Discontinue Subject
Hematologic Toxicity	1, 2, 3	No	N/A	N/A	N/A
	4	Yes	Toxicity resolves to $\leq$ Grade 1 or baseline	Restart at same dose for the following events: Grade 4 neutropenia lasting $\leq 7$ days, Grade 4 lymphopenia or leukopenia.	Toxicity dose not resolve within 6 weeks of last infusion. Permanent discontinuation must be considered for any severe or life-threatening event.

				For all other Grade 4 Hematologic toxicities treatment with nivolumab may not be restarted.	
Non-Hematologic Toxicity Note: Exception to be treated similar to Grade 1 toxicity: - Grade 2 alopecia - Grade 2 fatigue - Grade 3 rash in the absence of desquamation, without mucosal involvement, not requiring systemic steroids, and that resolves to Grade 1 within 14 days * See section 5.5. for immune-related AE's	1	No	N/A	N/A	N/A
	2	Consider holding for persistent symptoms	Toxicity resolves to ≤ Grade 1 or baseline	Restart at same dose	Toxicity does not resolve within 6 weeks of last infusion. Permanent discontinuation must be considered for any severe or life-threatening event.
	3	Yes	Toxicity resolves to ≤ Grade 1 or baseline	Restart at same dose	Toxicity does not resolve within 6 weeks of last infusion. Permanent discontinuation must be considered for any severe or life-threatening event.
	4	Yes	Discontinue treatment	Treatment with nivolumab may not be restarted	Toxicity does not resolve within 6 weeks of last infusion. Permanent discontinuation must be considered for any severe or life-threatening event.

Note: Subjects who experience a recurrence of the same severe or life-threatening AE at the same grade or greater treatment must be discontinued from study treatment.

If treatment for a participant needs to be held in a situation that is not the result of toxicity (non-toxicity scenario), treatment can be held for up to 8 weeks. If treatment needs to be held for a period greater than 8 weeks, the participant should be permanently discontinued from study treatment.

If treatment is held, regardless if for toxicity or non-toxicity, the missed dose is considered skipped and will not be made up.

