### 5.7.8. Procedures for Other Immune-Mediated Adverse Reactions, Including Ocular Manifestations

Nivolumab must be permanently discontinued for severe immune-mediated adverse reactions. Systemic corticosteroids treatment should be initiated at a dose of 1 to 2 mg/kg per day of prednisone or equivalent for severe immune-mediated adverse reactions.

Corticosteroid eye drops must be administered to subjects who develop uveitis, iritis, or episcleritis. Nivolumab must be permanently discontinued for immune-mediated ocular disease that is unresponsive to local immunosuppressive therapy.

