#### **8.4.3. Severity of Event**

Adverse events will be graded for severity according to the Common Terminology Criteria for Adverse Events (CTCAE) version 5.0

The following categories and definitions of intensity as determined by a physician must be used:

- Mild (Grade 1): Awareness of event but easily tolerated.
- Moderate (Grade 2): Discomfort enough to cause some interference with usual activity.
- Severe (Grade 3): Inability to carry out usual activity.
- Very Severe (Grade 4): Debilitating; significantly incapacitates subject despite symptomatic therapy.

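### For a recurrent or immune-mediated Grade 3 hematologic toxicity, the Table 2 row conflicts with the Table 2 note and with Section 5.7.8, and no precedence is stated

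*Combined protocol and SAP*

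**What the plan says.** Section 5.5 makes Table 2 binding: "Table 2 summarizes the dose administration guidance for nivolumab that must be implemented with the indicated related AEs". The first row of that table reads "Hematologic Toxicity 1, 2, 3 No N/A N/A N/A". For Grades 1 to 3 the answer to holding is therefore no, and the restart, nivolumab and discontinuation columns are all marked not applicable.

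The running text of Section 5.5 sets its own list of mandatory holds. It opens with "Treatment must be withheld for drug-related Grade 4 hematologic toxicities, non-hematological toxicity" of Grade 3 or higher, and closes with "immune-related toxicities, and severe or life-threatening AEs".

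The note below Table 2 adds a stopping rule for repeat events: "Subjects who experience a recurrence of the same severe or life-threatening AE at the same grade or greater treatment must be discontinued from study treatment".

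Section 5.7.8, which covers immune-mediated reactions without an algorithm of their own, states: "Nivolumab must be permanently discontinued for severe immune-mediated adverse reactions".

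Section 8.4.3, whose categories are mandatory for grading adverse events, ties the word to a grade: "Severe (Grade 3): Inability to carry out usual activity".

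**The concern.** These provisions are all phrased as obligations, and they meet on the same event. A site that reads only the hematologic row would infuse on schedule. A site that applies the note to a second episode, or Section 5.7.8 to an immune-mediated cytopenia, would stop treatment for good. Both could claim to be following the protocol, and under Section 11.3 each could be recorded as deviating from it.

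Patient safety is the main stake. There is also a consequence for the analysis. Safety and toxicity is a secondary endpoint (Section 2.3), and the synopsis lists five sites. If the response to a Grade 3 cytopenia depends on which passage a site follows, then exposure and the proportion stopping for toxicity partly reflect local reading of the text as well as the drug.

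**Working it through.** No formula applies and the plan gives no figure to reproduce. The check is a comparison of the passages.

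**Inputs.** The Table 2 hematologic row, the Section 5.5 text, the Table 2 note, Section 5.7.8, and the severity scale in Section 8.4.3.

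**Step 1: does Grade 3 count as severe?** Section 5.5 uses the word without defining it. The only definition in the protocol is in Section 8.4.3, where severe is Grade 3.

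**Step 2: is an immune-mediated cytopenia covered by Section 5.7.8?** Sections 5.7.1 to 5.7.7 deal in turn with lung, bowel, liver, skin, nerve, endocrine and kidney events. None is hematologic, so such an event falls by default into the residual category of Section 5.7.8.

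**Step 3: does any rule exempt hematologic events or rank itself?** The note stands under the whole table and excludes no row. Section 5.7.8 names no excluded organ system. The table's pointer to immune-related rules appears only in the non-hematologic row, and it refers to Section 5.5, not 5.7. No passage states an order of precedence.

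**Step 4: apply each rule to a drug-related Grade 3 hematologic event, taking severe as Grade 3.**

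| Event | Table 2 row | Closing phrase in 5.5 | Table 2 note | Section 5.7.8 |
|---|---|---|---|---|
| First, not immune-mediated | Do not hold; discontinuation N/A | Hold, if read broadly | Not triggered | Not triggered |
| Recurrent at Grade 3, not immune-mediated | Do not hold; discontinuation N/A | Hold, if read broadly | Discontinue | Not triggered |
| First, immune-mediated | Do not hold; discontinuation N/A | Hold, if read broadly | Not triggered | Discontinue permanently |

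In the second and third lines, continuing on schedule and mandatory discontinuation stand side by side. In the first line, the only conflict is between continuing and holding, and it depends on how the closing phrase is read.

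**Step 5: can the closing phrase be settled from the text?** Not fully. If it covers Grade 3 hematologic events, naming Grade 4 as the hematologic threshold in the same sentence becomes redundant. If it does not, and severe means Grade 3, the phrase adds nothing among drug-related events, because Grade 4 hematologic and Grade 3 or higher non-hematologic toxicity are already listed. If it is aimed at events regardless of cause, an unrelated Grade 3 cytopenia would be held while a drug-related one would not.

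**The case against.** A reader might infer that every drug-related Grade 3 hematologic event faces three incompatible orders: continue, hold or stop. The documents do not support that, for three reasons.

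- The Section 5.5 sentence that ends with the broad phrase begins by setting the hematologic hold threshold at Grade 4, exactly as Table 2 does. Letting the specific rule govern the general one removes the hold conflict for a first, non-immune event. This objection largely stands; what remains is an unlimited phrase that can be misread.
- Section 8.4.3 belongs to the part of the protocol on recording adverse events and describes severity by function. A Grade 3 laboratory value without symptoms may not meet that description. Section 5.5 does not treat severe and Grade 3 as plain synonyms either: the Grade 2 non-hematologic row also speaks of severe or life-threatening events. This stands as a limit on how many Grade 3 events are caught. It is also a reason to define the term, because sites could differ on whether a given Grade 3 cytopenia is severe.
- The two stopping rules are conditional, one on recurrence and the other on an immune-mediated cause.

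It can also be said that N/A does not mean never discontinue, and that Section 5.5 announces further dosing information later in the protocol, so the note and Section 5.7.8 merely supplement the row. That is a sensible reading, but the protocol does not state it. Preferring the specific rule does not decide the matter here: the row is specific to hematologic events, the note to recurrences, and Section 5.7.8 to immune-mediated events.

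Finally, placing immune-mediated cytopenias under Section 5.7.8 is an inference from the absence of a hematologic section, and several management figures in Section 5.7 are not reproduced in the available text and could not be checked.

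**Conclusion.** The point holds for recurrent and for immune-mediated Grade 3 hematologic events. The Table 2 row on one side, and the note or Section 5.7.8 on the other, give mandatory instructions that cannot both be followed, and nothing ranks them. This rests on two assumptions: that the Grade 3 event counts as severe, as Section 8.4.3 labels it, and that an immune-mediated cytopenia comes under Section 5.7.8 by default.

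For a first, non-immune event there is an ambiguity, not a firm contradiction, because the Section 5.5 text and Table 2 agree on Grade 4 as the hematologic threshold.

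The number of patients affected is unknown. The documents give no rate of Grade 3 hematologic toxicity, and none for its recurrent or immune-mediated subsets. No effect on the primary endpoint is shown. The case for correction is patient safety and consistent conduct across sites.

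**What to change.** Reconcile the Section 5.5 text, the Table 2 hematologic row, the Table 2 note and Section 5.7.8 so that each type of Grade 3 hematologic event (first, recurrent and immune-mediated) has a single action. State what *severe* means for dosing decisions, including whether it follows the CTCAE grade or the functional description in Section 8.4.3. State which passage prevails where they overlap. Which action applies is for the sponsor and investigators to decide; this review takes no view on it.

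The cost is a wording amendment with the IRB review that Section 10.2 requires, and notice to the sites. It adds no procedures and no patients.

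### Section 5.5 sets two limits for a drug-related toxicity hold, 8 weeks in the text and 6 weeks in Table 2, and they conflict for restartable, non-immune toxicities that resolve on days 43-56

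*Combined protocol and SAP*

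**What the plan says.** The text of section 5.5 first lists what triggers a hold: "Treatment must be withheld for drug-related Grade 4 hematologic toxicities, non-hematological toxicity" of Grade 3 or higher, selected immune-related toxicities of Grade 2 or higher, and severe or life-threatening events. It then sets the limit: "Treatment can be held for up to 8 weeks from date of last treatment". The permanent stop comes only beyond that point: "if treatment must be withheld for greater than 8 weeks, participant must be permanently discontinued from study treatment". Treatment may resume once the event is back to Grade 1 or less, or to baseline, with listed exceptions.

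The same section introduces the table in binding terms: "Table 2 summarizes the dose administration guidance for nivolumab that must be implemented with the indicated related AEs". In the Discontinue Subject column, the Grade 4 hematologic row reads "Toxicity dose not resolve within 6 weeks of last infusion" (sic). The Grade 2, 3 and 4 non-hematologic rows read "Toxicity does not resolve within 6 weeks of last infusion".

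Table 2 also limits which events may restart at all. In the Grade 4 hematologic row: "Restart at same dose for the following events: Grade 4 neutropenia lasting" 7 days or less, and Grade 4 lymphopenia or leukopenia. Then: "For all other Grade 4 Hematologic toxicities treatment with nivolumab may not be restarted". Grade 4 non-hematologic toxicity may not restart either. A note in the non-hematologic row sends the reader to section 5.5 for immune-related events.

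A separate 8-week limit, for holds not caused by toxicity, follows the table. A held dose counts as skipped and is not made up.

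**The concern.** Both limits run from the last dose, and both apply to drug-related Grade 4 hematologic toxicity and to non-hematologic toxicity of Grade 3 or higher. One permits up to 8 weeks; the other ends treatment at 6 weeks if the toxicity persists. No sentence says which governs or how they fit together.

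At stake is whether a particular patient receives more nivolumab. Section 11.3 counts any noncompliance with the protocol as a deviation to be reported to the IRB. So the same infusion can be compliant under the text and a reportable deviation under the table. The error can also run in the unsafe direction: a site that relies on the text may re-dose a patient whom the table says to stop.

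**Working it through.** **Inputs.** Text limit: 8 weeks from last dose (5.5). Table limit: 6 weeks from last infusion (5.5, Table 2). Schedule: one dose every 4 weeks, 12 doses (3.4). Skipped doses are not made up (5.5).

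**Step 1, the window.** 6 × 7 = 42 days; 8 × 7 = 56 days; 56 − 42 = 14 days. A toxicity that resolves by day 42 may restart under both rules. From day 57 both rules stop treatment. On days 43 to 56 the text permits a restart and Table 2 requires a stop.

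**Step 2, the dosing slot.** Nominal slots after the last dose fall on days 28 and 56. With the day-28 dose skipped, the next slot is day 56, the last day the text allows. A toxicity first found at the day-28 visit has 42 − 28 = 14 days to resolve under the table and 56 − 28 = 28 days under the text.

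**Step 3, which rows are affected.**

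| Toxicity | Table 2 restart? | Days 43-56, text limit | Days 43-56, Table 2 | Does 6 v 8 weeks matter? |
|---|---|---|---|---|
| Grade 3 non-hematologic | Yes | Restart | Stop | Yes |
| Grade 2 non-hematologic, if held | Yes | Restart | Stop | Yes, by inference |
| Grade 4 lymphopenia or leukopenia | Yes | Restart | Stop | Yes |
| Grade 4 neutropenia, 7 days or less | Yes | Restart | Stop | In principle |
| Other Grade 4 hematologic | No | – | Stop on any day | No |
| Grade 4 non-hematologic | No | – | Stop on any day | No |

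Grade 2 is by inference because the table only suggests considering a hold, and non-immune Grade 2 events are not in the text's list of mandatory holds. Brief neutropenia is in principle only: Grade 4 must last 7 days or less, yet return to Grade 1 or baseline only after day 42.

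**Step 4, immune-related events.** The note in Table 2 arguably takes these out of the 6-week rule and back to the 5.5 text. Dermatitis and endocrinopathy are presumed immune-mediated unless another cause is found (5.7.4, 5.7.6), and severe immune-mediated reactions under 5.7.8 are a permanent stop anyway. They are therefore outside the conflict as stated here.

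**Step 5, doses at stake for one patient.** If dose k was the last given and dose k+1 is skipped, at most 12 − (k + 1) = 11 − k doses remain. That is 10 for k = 1 and 1 for k = 10 under the text, assuming no later skip or stop, and 0 under Table 2. This is a ceiling for one patient and says nothing about how often the case arises.

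**The case against.** The strongest reply is that the two limits can be obeyed together. The text caps time off drug, the table caps time to resolution, and the table is mandatory. A careful site would stop at week 6 if the toxicity is unresolved and otherwise re-dose by week 8. That reading is workable, and the fix below adopts it. But the text is more than a permissive cap: it has its own resume rule and its own mandatory stop, which comes only after 8 weeks. Nothing ranks one rule over the other. Nor can the 8 weeks in the text be read as the limit for non-toxicity holds, because that limit is stated separately after the table.

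The reply that the affected group is small also stands.

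A reader might infer three stronger points, which the documents do not support:

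- *That rates of stopping for toxicity will not be comparable between the five sites, to the harm of a trial result.* Sites may differ, but sections 2.3 and 9.1 plan no between-site comparison and no discontinuation-rate endpoint. Safety is assessed by CTCAE in a single arm.
- *That the visit schedule cannot show whether a toxicity resolved by day 42.* Sections 8.3 and 8.4.5 require events to be followed to resolution or stabilization. Many Grade 2-3 non-hematologic events are judged by symptoms, and nothing prevents an unscheduled check.
- *That the 6-week limit should simply be imposed on every toxicity.* Section 5.5 keeps open retreatment for persistent Grade 1 pneumonitis after a steroid taper of at least 1 month, with the lead investigator's approval. Taking a month as 30 days, a taper begun after day 42 − 30 = 12 could not finish by day 42. A blanket limit would close that route.

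**Conclusion.** The inconsistency is real and narrow. For non-immune toxicities that Table 2 lets restart, resolution on days 43-56 permits re-dosing at the week-8 slot under the text and ends treatment under the table. The consequence is limited to who is re-dosed and whether that dose is a deviation.

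A reader might infer that the primary endpoint is at risk. It is not. Sections 5.5.1 and 7.2 keep patients who stop nivolumab in follow-up, and no sample-size, power or alpha figure depends on the hold rule.

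The conclusion assumes that Table 2's note does take immune-related events out of the 6-week rule. The immune-event management figures are not available in the text reviewed, so their hold and resume rules could not be checked. The documents give no basis for a patient count. Because the conflict is between two operative stopping rules for study drug and is cheap to remove, it should be corrected.

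**What to change.** Add to the 5.5 text:

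> *For the toxicities in Table 2 other than immune-related AEs, the toxicity must resolve to the level required for restart within 6 weeks of the last infusion, and re-dosing must occur within 8 weeks of the last infusion; otherwise study treatment is permanently discontinued. Immune-related AEs follow the 8-week hold and the resumption exceptions in this section.*

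This loosens no limit in Table 2 for the non-immune toxicities, leaves the pneumonitis route open, and settles what the note on immune-related events means. The permanent-stop rules in 5.7 remain in place.

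If the sponsor confirms that 8 weeks was intended throughout, change 6 weeks to 8 weeks wherever it appears in Table 2 instead. That fits the next 4-weekly slot after one skipped dose. In rows where restart is barred, the change has no effect.

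Either option costs one short amendment and a notice to sites. The first may mean a few extra permanent stops compared with following the text alone. The second tolerates an unresolved toxicity for up to 14 days longer before treatment must end. No new visit or laboratory test is needed.
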